### 13.10.6. Detailed Dose Escalation /De-escalation Scheme for mTPI Design for Sasanlimab + Axitinib + SEA-TGT

A safe dose will be determined using the adaptive mTPI design. The mTPI design uses a Bayesian statistics framework and a beta/binomial hierarchical model to compute the posterior probability of 3 dosing intervals that reflect the relative difference between the toxicity rate of each dose level to the target probability ( $p_T$ ) rate ( $p_T=0.30$ ). If the toxicity rate of the currently used dose level is far smaller than  $p_T$ , the mTPI will recommend escalating the dose level; if it is close to  $p_T$ , the mTPI will recommend continuing at the current dose; if it is far greater than  $p_T$ , the mTPI will recommend deescalating the dose level. These rules are conceptually similar to those used by the 3+3 design, except the decisions of an mTPI design are based on posterior probabilities calculated under a coherent probability model. As shown by Ji and Wang, mTPI design is more efficient and safer than the 3+3 design. They considered 42 scenarios to cover a wide range of practical dose-response shapes, and concluded that the 3 + 3 design was more likely to treat participants at toxic doses above the MTD and less likely to identify the true MTD than the mTPI design. For example, the 3 + 3 design exhibited a lower overall toxicity percentage than the mTPI design in only 1 of 42 scenarios.

Decision rules are based on calculating unit probability mass (UPM) of 3 dosing intervals corresponding to under, proper, and overdosing in terms of toxicity ([Table 30](#)). Specifically, the underdosing interval is defined as  $[0, p_T-e_1)$ , the overdosing interval  $(p_T+e_2, 1]$ , and the proper-dosing interval  $[p_T- e_1, p_T+ e_2)$ , where  $e_1$  and  $e_2$  are small fractions. Based on the projected safety profile,  $e_1$  is selected as 0.05, and  $e_2$  is selected as 0.05. Therefore, the target interval for the DLT rate is  $[0.25, 0.35)$ . The 3 dosing intervals are associated with 3 different dose-escalation decisions. The underdosing interval corresponds to a dose escalation (E), overdosing corresponds to dose de-escalation (D), and proper dosing corresponds to staying at the current dose (S). Given a dosing interval and a probability distribution, the UPM of that dosing interval is defined as the probability of a participant belonging to that dosing interval divided by the length of the dosing interval. The mTPI design calculates the UPMs for the 3 dosing intervals, and the one with the largest UPM informs the corresponding dose-finding decision, which is the dose level to be used for future participants. For example, if the underdosing interval has the largest UPM, the decision will be to escalate, and the next 3-4 participants will be treated at the next higher dose level. Simulations have demonstrated that the decision based on UPM is optimal in that it minimizes a posterior expected loss (ie, minimizes the chance of making a wrong dosing decision).

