**Table 26. Sub-Study B, Phase 1b, Triplet Cohorts Dose Levels**

Dose Level	Sasanlimab	Axitinib*	SEA-TGT
1	CCI	3 or 5 mg BID	3 mg/kg IV Q3W
0 (Starting Dose)	CCI	3 or 5 mg BID	1 mg/kg IV Q3W
-1	CCI	3 or 5 mg BID	0.3 mg/kg IV Q3W

DLT period = 1 cycle of 21 days.  
 mTPI dose finding schema will be used for dose finding.  
 \*Axitinib dose will be determined by the doublet cohorts and will be fixed in the triplet cohorts.

A minimum of 3 DLT-evaluable participants will be required in each cohort; additional participants will be enrolled in the specific enrollment cohort to replace participants who are not considered DLT-evaluable, where required. When all DLT-evaluable participants treated in a given enrollment cohort have completed the DLT observation period or experienced a DLT, whichever occurs first, the posterior probabilities for the risk of DLT for new

participants at different dose levels for the combination of interest will be evaluated. If the toxicity rate of the currently used dose level is far smaller than the target probability of toxicity (pT) of 0.30, the mTPI will recommend escalating the dose level; if it is close to pT, the mTPI will recommend continuing at the current dose; if it is far greater than pT, the mTPI will recommend de-escalating the dose level. The mTPI dose de-escalation/escalation recommendation will be based on the estimated toxicity rate and 3 intervals (underdosing, target toxicity, and excessive toxicity) as shown below:

- If current dose is in the underdosing [0, 0.25) toxicity interval: escalate to next higher dose;
- If current dose is in the target toxicity [0.25, 0.35) toxicity interval: stay at current dose;
- If current dose is in the excessive toxicity or overdosing [0.35, 1] toxicity interval: de-escalate to a lower dose

Refer to [Section 13.9](#) and [Section 13.10.6](#) for more details on the mTPI design and decision rules.

The number of participants to be enrolled in Phase 1b will depend upon the observed safety profile, which will determine the number of participants at each dose level and the number of dose levels explored.

It is anticipated that up to approximately 20 total participants will be enrolled in Phase 1b starting with Dose Level 0 of the doublet cohorts, and including the triplet cohorts.

An RP2D below the MTD, or highest safe dose tested, may be determined based on other safety, clinical activity, PK, and pharmacodynamic data.

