**Table 30. Dose Finding Rules**

		Number of Participants Treated at Current Dose															
r/n		3	4	5	6	7	8	9	10	11	12	13	14	15	16	17	18
Number of DLTs	0	E	E	E	E	E	E	E	E	E	E	E	E	E	E	E	E
	1	S	S	S	E	E	E	E	E	E	E	E	E	E	E	E	E
	2	D	S	S	S	S	S	S	S	E	E	E	E	E	E	E	E
	3	DU	DU	D	S	S	S	S	S	S	S	S	S	S	S	E	E
	4		DU	DU	DU	D	D	S	S	S	S	S	S	S	S	S	S
	5			DU	DU	DU	DU	DU	D	S	S	S	S	S	S	S	S
	6				DU	DU	DU	DU	DU	DU	D	S	S	S	S	S	S
	7					DU	DU	DU	DU	DU	DU	DU	D	S	S	S	S
	8						DU	DU	DU	DU	DU	DU	DU	DU	DU	D	S
	9							DU	DU	DU	DU	DU	DU	DU	DU	DU	DU
	10								DU	DU	DU	DU	DU	DU	DU	DU	DU
	11									DU	DU	DU	DU	DU	DU	DU	DU
	12										DU	DU	DU	DU	DU	DU	DU
	13											DU	DU	DU	DU	DU	DU
	14												DU	DU	DU	DU	DU
	15													DU	DU	DU	DU
	16														DU	DU	DU
	17															DU	DU
18																DU	

**E** = Escalate to the next higher dose level  
**S** = Stay at the current dose level  
**D** = De-escalate to the next lower dose level  
**DU** = The current dose level is unacceptably toxic and should be eliminated from further dose finding  
**DLTs** = Dose Limiting Toxicities; Targeted DLT rate=30%

Select escalation/de-escalation algorithms for total number of participants treated at the current dose level (current and previous cohorts):

With 3 participants treated at current dose level

- 0 DLT: escalate
- 1 DLT: remain at the same dose
- 2 DLTs: de-escalate
- 3 DLTs: de-escalate and consider current dose as intolerable

With 6 participants treated at current dose level

- 0-1 DLT: escalate
- 2-3 DLTs: remain at the same dose
- 4-6 DLTs: de-escalate and consider current dose as intolerable

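### Sub-Study B, Table 30: the cell for 3 DLTs in 16 participants is printed Stay, while the largest-UPM rule that the table is said to implement gives Escalate

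*Protocol*

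**What the plan says.** Protocol Section 13.10.6 describes "a beta/binomial hierarchical model to compute the posterior probability of 3 dosing intervals" and sets the three intervals by taking e1 = e2 = 0.05 around a target of 0.30. The unit probability mass (UPM) of an interval is its probability "divided by the length of the dosing interval". The decision rule is: "The mTPI design calculates the UPMs for the 3 dosing intervals, and the one with the largest UPM informs the corresponding dose-finding decision". Underdosing maps to escalation (E), proper dosing to staying (S) and overdosing to de-escalation (D).

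Section 13.4.1 gives the same intervals, for example "If current dose is in the target toxicity [0.25, 0.35) toxicity interval: stay at current dose". Section 13.9.1.2 refers to the table in Section 13.10.6 as holding decisions calculated beforehand under the mTPI design.

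That table, "Table 30. Dose Finding Rules", carries the note "Targeted DLT rate=30"% and covers 3 to 18 participants at the current dose. Its row for 3 DLTs prints S at 15 participants, S at 16, and E at 17 and 18. Neither the Beta prior nor the probability cut-off behind the DU entries is given.

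**The concern.** If a decision table is the output of a stated rule, each cell should follow from that rule. At 3 DLTs in 16 the text and the table point to different actions: the text to E, the table to S. Nothing in the protocol says that this cell was set by hand or which source prevails.

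What is at stake is internal consistency in a dose-finding rule. The same data should not produce one recommendation when the team reads the table and another when it runs the algorithm.

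**Working it through.** **Inputs**
- Target 0.30 with e1 = e2 = 0.05 (Section 13.10.6). The intervals are therefore [0, 0.25), [0.25, 0.35) and 0.35 to 1, with lengths 0.25, 0.10 and 0.65.
- Decision: the interval with the largest UPM (Section 13.10.6).
- Assumption: a Beta(1,1) prior. The protocol names a beta/binomial model but gives no prior parameters.
- Assumption: DU when Pr(DLT rate > 0.30 | data) > 0.95. The cut-off is not stated, and it does not affect the 3/16 cell.

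**Formulas.** With x DLTs in n participants, the posterior is Beta(1 + x, 1 + n − x) with distribution function F. Then:
- UPM(E) = F(0.25) / 0.25
- UPM(S) = [F(0.35) − F(0.25)] / 0.10
- UPM(D) = [1 − F(0.35)] / 0.65

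**Step 1: reproduce the table.** Table 30 has 184 printed cells (n = 3 to 18, 0 to n DLTs). Under the two assumptions, 183 agree with the rule, including every D and DU entry. The one that does not is 3/16.

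**Step 2: the cell itself.** For x = 3 and n = 16 the posterior is Beta(4, 14). Its distribution function at p equals P(Bin(17, p) ≥ 4), which gives F(0.25) = 0.6470 and F(0.35) = 0.8972.
- UPM(E) = 0.6470 / 0.25 = 2.588
- UPM(S) = (0.8972 − 0.6470) / 0.10 = 2.502
- UPM(D) = (1 − 0.8972) / 0.65 = 0.158

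The largest is underdosing, so the rule gives E.

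**Step 3: compare with nearby cells and other close calls.**

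| DLTs / n | UPM(E) | UPM(S) | Rule | Printed |
|---|---|---|---|---|
| 3/15 | 2.380 | 2.711 | S | S |
| 3/16 | 2.588 | 2.502 | E | **S** |
| 3/17 | 2.777 | 2.274 | E | E |
| 2/11 | 2.437 | 2.394 | E | E |
| 1/6 | 2.220 | 2.111 | E | E |

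The margin at 3/16 is 2.588 − 2.502 = 0.086. At 2/11 it is 2.437 − 2.394 = 0.043, and that cell is printed E. Rounding, or a tie-break towards caution, would have changed 2/11 first.

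**Step 4: could another prior explain it?**
- Beta(0.5, 0.5), Beta(0.005, 0.005), Beta(0.3, 0.7) and Beta(0.6, 1.4) all give E at 3/16, with UPM(E) from 2.82 to 3.05 against UPM(S) from 1.75 to 2.13.
- Beta(1.1, 1) does give S at 3/16, but it then disagrees with five other printed cells: 1/6, 2/11, 3/6, 7/14 and 7/15.
- Over a grid of Beta(a, b) priors in steps of 0.05, with a from 0.05 to just under 4 and b from 0.05 to just under 8, none gives S at 3/16 while keeping the printed E at 2/11.

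**Step 5: can the cell be reached?** In Phase 1b, yes, but rarely. At a triplet level below the top one, the sequence 1/4, 2/8, 3/12 is Stay at each look in Table 30 and can lead to 3/16. With at least 3 participants first treated in the doublet, that makes 3 + 16 = 19 of the roughly 20 planned.

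**The case against.** **The prior is not stated, so the rule cannot be said to give E.** The missing parameters are a real limit on the check, but they do not rescue the cell. Every prior tried that gives S at 3/16 breaks other printed cells.

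**It may be a misread character.** The text was extracted from a PDF. The row has all 16 entries, so no column has shifted, but a single wrong letter cannot be excluded from the text alone. The worked examples below the table cover only 3 and 6 participants, so they do not test this cell. This objection stands, and it is why the fix starts with the source table.

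**The table guides and does not bind.** This also stands. Section 13.4.1 describes enrolment as guided by the mTPI and speaks of recommendations, and the recommended Phase 2 dose may rest on other data. A reader might infer that dosing decisions would be wrong as a direct result of this cell. The documents do not support that.

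**It almost never matters.** Largely right. At the top triplet level there is nothing to escalate to, and the doublet starts at its higher axitinib level. A reader might also infer that the cell comes into play in Phase 2, because Section 13.4.1 continues the mTPI review of cumulative DLTs there. The only action named for that stage is to explore the next lower level if the dose proves too toxic (a DLT rate of 35% or more). The rate at 3/16 is about 19%, so E versus S changes nothing in Phase 2.

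**The printed entry is the safer one.** Stay is the more cautious of the two, so the discrepancy gives no ground for inferring added risk to participants.

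**Conclusion.** The point holds as an internal inconsistency confined to one of 184 cells. Table 30 prints Stay for 3 DLTs in 16, while the rule that it is said to implement gives underdosing the largest UPM there (2.588, against 2.502 and 0.158).

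The conclusion rests on three assumptions: a Beta(1,1) prior, a 0.95 cut-off for DU (needed to match the DU cells but not for 3/16), and a faithfully extracted cell. The first is well supported by the match of all the other cells and by the failure of every alternative prior tried.

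The importance is minor. The cell can be reached only at a non-top Phase 1b level, by a sequence that uses nearly the whole phase. Two stronger readings are tempting. One is that the table as a whole is unreliable, but every other cell agrees with the rule. The other is that Escalate is the correct decision at 3/16. The documents show only that text and table disagree, not which decision is clinically right. The unstated prior and cut-off are detail that a statistical analysis plan may carry, and they are not part of this point.

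**What to change.** Check the 3/16 entry against the original calculation or source table. Then reconcile Table 30 with the rule in Section 13.10.6 in one of two ways: make the cell agree with the stated rule, or add a sentence saying that the cell is a deliberate departure from it. Which decision applies is for the sponsor to settle.

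The cost is one table cell or one sentence. Sample size, dose levels and the rest of the table are unaffected.

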**Table 30. Dose Finding Rules**

		Number of Participants Treated at Current Dose															
r/n		3	4	5	6	7	8	9	10	11	12	13	14	15	16	17	18
Number of DLTs	0	E	E	E	E	E	E	E	E	E	E	E	E	E	E	E	E
	1	S	S	S	E	E	E	E	E	E	E	E	E	E	E	E	E
	2	D	S	S	S	S	S	S	S	E	E	E	E	E	E	E	E
	3	DU	DU	D	S	S	S	S	S	S	S	S	S	S	S	E	E
	4		DU	DU	DU	D	D	S	S	S	S	S	S	S	S	S	S
	5			DU	DU	DU	DU	DU	D	S	S	S	S	S	S	S	S
	6				DU	DU	DU	DU	DU	DU	D	S	S	S	S	S	S
	7					DU	DU	DU	DU	DU	DU	DU	D	S	S	S	S
	8						DU	DU	DU	DU	DU	DU	DU	DU	DU	D	S
	9							DU	DU	DU	DU	DU	DU	DU	DU	DU	DU
	10								DU	DU	DU	DU	DU	DU	DU	DU	DU
	11									DU	DU	DU	DU	DU	DU	DU	DU
	12										DU	DU	DU	DU	DU	DU	DU
	13											DU	DU	DU	DU	DU	DU
	14												DU	DU	DU	DU	DU
	15													DU	DU	DU	DU
	16														DU	DU	DU
	17															DU	DU
18																DU	

**E** = Escalate to the next higher dose level  
**S** = Stay at the current dose level  
**D** = De-escalate to the next lower dose level  
**DU** = The current dose level is unacceptably toxic and should be eliminated from further dose finding  
**DLTs** = Dose Limiting Toxicities; Targeted DLT rate=30%

Select escalation/de-escalation algorithms for total number of participants treated at the current dose level (current and previous cohorts):

With 3 participants treated at current dose level

- 0 DLT: escalate
- 1 DLT: remain at the same dose
- 2 DLTs: de-escalate
- 3 DLTs: de-escalate and consider current dose as intolerable

With 6 participants treated at current dose level

- 0-1 DLT: escalate
- 2-3 DLTs: remain at the same dose
- 4-6 DLTs: de-escalate and consider current dose as intolerable
